3.4.5 Potential Drug Interactions

Cytochrome P450 (CYP): Data from a clinical drug interaction study (Study XL184-008) show that clinically relevant steady-state concentrations of cabozantinib appear to have no marked

effect on the area under the plasma drug concentration time curve (AUC) of co-administered rosiglitazone, a CYP2C8 substrate. Therefore, cabozantinib is not anticipated to markedly inhibit CYP2C8 in the clinic, and by inference, is not anticipated to markedly inhibit other CYP450 isozymes that have lower $[I]/K_i$ values compared with CYP2C8 (ie, CYP2C9, CYP2C19, CYP2D6, CYP1A2, and CYP3A4). In vitro data indicate that cabozantinib is unlikely to induce cytochrome P450 enzymes, except for possible induction of CYP1A1 at high cabozantinib concentrations (30 μ M).

Cabozantinib is a CYP3A4 substrate and a weak substrate for CYP2C9 (but not a CYP2D6, CYP2C8, CYP2C19, CYP2B6, or CYP1A2 substrate), based on data from in vitro studies. Results from a clinical pharmacology study, XL184-006, showed that concurrent administration of cabozantinib with the strong CYP3A4 inducer, rifampin, resulted in an approximately 77% reduction in cabozantinib exposure (AUC values) after a single dose of cabozantinib in healthy volunteers. Chronic co-administration of cabozantinib with strong inducers of the CYP3A4 family (eg, phenytoin, carbamazepine, rifampin, rifabutin, rifapentine, phenobarbital, and St. John's Wort) may significantly decrease cabozantinib concentrations. The chronic use of strong CYP3A4 inducers should be avoided. Other drugs that induce CYP3A4 should be used with caution because these drugs have the potential to decrease exposure (AUC) to cabozantinib. Selection of alternate concomitant medications with no or minimal CYP3A4 enzyme induction potential is recommended.

Results from a clinical pharmacology study, XL184-007, showed that concurrent administration of cabozantinib with the strong CYP3A4 inhibitor, ketoconazole, resulted in a 38% increase in the cabozantinib exposure (AUC values) after a single dose of cabozantinib in healthy volunteers. Co-administration of cabozantinib with strong inhibitors of the CYP3A4 family (eg, ketoconazole, itraconazole, clarithromycin, indinavir, nefazodone, nelfinavir, and ritonavir) may increase cabozantinib concentrations. Grapefruit and Seville oranges may also increase plasma concentrations of cabozantinib and should be avoided. Strong CYP3A4 inhibitors should be avoided and other drugs that inhibit CYP3A4 should be used with caution because these drugs have the potential to increase exposure (AUC) to cabozantinib. Selection of alternate concomitant medications with no or minimal CYP3A4 enzyme inhibition potential is recommended.

In addition, cimetidine should be avoided because of its potential to interfere with CYP3A4 mediated metabolism of cabozantinib.

Please refer to the drug interaction tables at the following websites for lists of substrates, inducers, and inhibitors of selected CYP450 isozyme pathways:

[Http://medicine.iupui.edu/clinpharm/ddis/table.aspx](http://medicine.iupui.edu/clinpharm/ddis/table.aspx)

<http://www.fda.gov/Drugs/DevelopmentApprovalProcess/DevelopmentResources/DrugInteractionsLabeling/ucm080499.htm>

Protein Binding: Cabozantinib is highly bound ($\geq 99.7\%$) to human plasma proteins. Therefore, highly protein bound drugs should be used with caution with cabozantinib because there is a potential displacement interaction that could increase free concentrations of cabozantinib and/or a co-administered highly protein-bound drug (and a corresponding increase in pharmacologic effect).

Other Interactions:

Food may increase exposure levels of cabozantinib by 57%, fasting recommendations should be followed. Subjects should fast (with the exception of water) for at least 2 hours before taking their dose of cabozantinib. After the 2-hour fast, subjects are to take cabozantinib with a full glass of water (minimum of 8 oz or 240 mL) with no more food intake for one hour post-dose.

In vitro data suggest that cabozantinib is unlikely to be a substrate for P-glycoprotein, but it does appear to have the potential to inhibit the P-glycoprotein transport activity. Therefore, cabozantinib may have the potential to increase plasma concentrations of co-administered substrates of P-glycoprotein.

Cabozantinib was shown to be a substrate of drug transporter MRP2 in an in vitro assay. Administration of MRP2 inhibitors to subjects may result in increases in cabozantinib plasma concentrations.

Additional details regarding potential drug interactions with cabozantinib can be found in the investigator brochure.

3.5 Compliance

Drug accountability and subject compliance will be assessed with drug dispensing and return records.

3.6 Study Drug Accountability

The investigator will maintain accurate records of receipt of all cabozantinib, including dates of receipt. In addition, accurate records will be kept regarding when and how much study treatment is dispensed and used by each subject in the study. Reasons for deviation from the expected dispensing regimen must also be recorded. At completion of the study, to satisfy regulatory requirements regarding drug accountability, all unused cabozantinib will be reconciled and destroyed in accordance with applicable state and federal regulations.

4 STUDY POPULATION

4.1 Inclusion Criteria

A subject must fully meet all of the following criteria to be eligible for the study:

1. The subject has a histologic or cytologic diagnosis of squamous cell carcinoma of the oral cavity, oropharynx, paranasal sinuses, hypopharynx, nasopharynx or larynx. Squamous cell carcinoma of unknown primary in cervical lymph node can be included only if HPV status is positive.
2. Patients must have refractory, recurrent or metastatic disease, which is deemed to be inoperable.
3. In case patients received prior systemic therapy within the definitive or metastatic setting, disease progression must be documented following prior therapy; this can be in the recurrent or metastatic setting or in the concurrent setting.
4. Measurable disease per RECIST 1.1 as determined by the investigator;
5. A maximum of one prior radiotherapy regimen, curative or palliative, to the head and neck is allowed. If the radiation is combined with chemotherapy, a minimum of 4 months must elapse between the end of radiotherapy and registration. If the radiation is given alone, a minimum of 8 weeks must elapse between the end of radiotherapy and registration. A minimum of 3 weeks must elapse between prior radiation to other areas and registration. Treatment areas should be healed with no sequelae from RT that would predispose to fistula formation.
6. The subject has had an assessment of all known disease sites eg, by computerized tomography (CT) scan, magnetic resonance imaging (MRI), bone scan or PET/CT as appropriate, within 28 days before the first dose of cabozantinib;
7. The subject is ≥ 18 years old on the day of consent;

8. Life expectancy of greater than 3 months.
9. The subject has an Eastern Cooperative Oncology Group (ECOG) performance status of 0 or 1;
10. Recovery to baseline or \leq Grade 1 CTCAE v.4.0 from toxicities related to any prior treatments, unless AE(s) are clinically nonsignificant and/or stable on supportive therapy;
11. The subject has organ and marrow function and laboratory values as follows within 7 days before the first dose of cabozantinib:
 - a. The ANC \geq 1000/mm³ without colony stimulating factor support;
 - b. Platelets \geq 100,000/mm³;
 - c. Hemoglobin \geq 9 g/dL;
 - d. Bilirubin \leq 1.5 \times the ULN. For subjects with known Gilbert's disease, bilirubin \leq 3.0 mg/dL;
 - e. Serum albumin \geq 2.8 g/dl;
 - f. Serum creatinine \leq 1.5 \times ULN or creatinine clearance (CrCl) \geq 40 mL/min. For creatinine clearance estimation, the Cockcroft and Gault equation should be used:
 - i. Male: CrCl (mL/min) = $(140 - \text{age}) \times \text{wt (kg)} / (\text{serum creatinine} \times 72)$;
 - ii. Female: Multiply above result by 0.85;
 - g. ALT and AST \leq 2.0 \times ULN;
 - h. Lipase $<$ 2.0 x the upper limit of normal and no radiologic or clinical evidence of pancreatitis;
 - i. UPCR \leq 1;
 - j. Serum phosphorus, calcium, magnesium and potassium \geq LLN.
12. The subject is capable of understanding and complying with the protocol requirements and has signed the informed consent document;

13. Sexually active subjects (men and women) must agree to use medically accepted barrier methods of contraception (eg, male or female condom) during the course of the study and for 4 months after the last dose of study drug(s), even if oral contraceptives are also used. All subjects of reproductive potential must agree to use both a barrier method and a second method of birth control during the course of the study and for 4 months after the last dose of study drug(s);
14. Female subjects of childbearing potential must not be pregnant at screening. Females of childbearing potential are defined as premenopausal females capable of becoming pregnant (ie, females who have had any evidence of menses in the past 12 months, with the exception of those who had prior hysterectomy). However, women who have been amenorrheic for 12 or more months are still considered to be of childbearing potential if the amenorrhea is possibly due to prior chemotherapy, antiestrogens, low body weight, ovarian suppression or other reasons.
15. A male participant must agree to use a contraception as detailed in this protocol during the treatment period and for at least during the active treatment plus an additional 90 days (a spermatogenesis cycle) for study treatments with evidence of genotoxicity at any dose] after the last dose of study treatment and refrain from donating sperm during this period.

○ **Exclusion Criteria**

A subject who meets any of the following criteria is ineligible for the study:

1. Patients who have HPV negative squamous cell carcinoma of unknown primary in cervical lymph node.
2. The subject has received cytotoxic chemotherapy (including investigational cytotoxic chemotherapy) or biologic agents (eg, cytokines or antibodies) within 4 weeks, or nitrosoureas/mitomycin C within 6 weeks before the first dose of study treatment;
3. Prior treatment with cabozantinib or pembrolizumab; or any prior immunotherapy for treating squamous cell carcinoma of the head and neck;
4. Radiation therapy for bone metastasis within 2 weeks, any other external radiation therapy within 4 weeks before the first dose of study treatment. Systemic treatment with radionuclides within 6 weeks before the first dose of study treatment. Subjects with clinically relevant ongoing complications from prior radiation therapy are not eligible;

5. Receipt of any type of small molecule kinase inhibitor (including investigational kinase inhibitor) within 14 days before the first dose of study treatment;
6. The subject has received any other type of investigational agent within 28 days or 5 half-lives, whichever is shorter, before the first dose of study treatment;
7. Known brain metastases or cranial epidural disease unless adequately treated with radiotherapy and/or surgery (including radiosurgery) and stable for at least 4 weeks before the first dose of study treatment. Eligible subjects must be neurologically asymptomatic and without corticosteroid treatment at the time of the start of study treatment;
8. The subject has prothrombin time (PT)/INR or partial thromboplastin time (PTT) test $\geq 1.3 \times$ the laboratory ULN within 7 days before the first dose of study treatment;
9. Concomitant anticoagulation at therapeutic doses with oral anticoagulants (eg, warfarin, direct thrombin and Factor Xa inhibitors) or platelet inhibitors (eg, clopidogrel);

Note: Low-dose aspirin for cardioprotection (per local applicable guidelines), low-dose warfarin (< 1 mg/day), and low dose, low molecular weight heparins (LMWH) are permitted. Anticoagulation with therapeutic doses of LMWH is allowed in subjects who are on a stable dose of LMWH for at least 6 weeks before first dose of study treatment, and who have had no clinically significant hemorrhagic complications from the anticoagulation regimen or the tumor.

10. The subject has experienced any of the following:
 - a. clinically-significant GI bleeding within 6 months before the first dose of study treatment;
 - b. hemoptysis of ≥ 0.5 teaspoon (2.5ml) of red blood within 3 months before the first dose of study treatment;
 - c. any other signs indicative of pulmonary hemorrhage within 3 months before the first dose of study treatment.
11. The subject has radiographic evidence of cavitating pulmonary lesion(s);
12. The subject has tumor invading or encasing any major blood vessels;

13. The subject has evidence of tumor invading the GI tract (esophagus, stomach, small or large bowel, rectum or anus), or any evidence of endotracheal or endobronchial tumor within 28 days before the first dose of cabozantinib;
14. The subject has uncontrolled, significant intercurrent or recent illness including, but not limited to, the following conditions:
 - a. Cardiovascular disorders including:
 - i. Congestive heart failure (CHF): New York Heart Association (NYHA) Class III (moderate) or Class IV (severe) at the time of screening;
 - ii. Concurrent uncontrolled hypertension defined as sustained blood pressure (BP) > 150 mm Hg systolic or > 100 mm Hg diastolic despite optimal antihypertensive treatment within 7 days of the first dose of study treatment;
 - iii. Any history of congenital long QT syndrome;
 - iv. Any of the following within 6 months before the first dose of study treatment:
 - unstable angina pectoris;
 - clinically-significant cardiac arrhythmias;
 - stroke (including transient ischemic attack (TIA), or other ischemic event);
 - myocardial infarction;
 - b. GI disorders particularly those associated with a high risk of perforation or fistula formation including:
 - i. Tumors invading the GI tract, active peptic ulcer disease, inflammatory bowel disease (eg, Crohn's disease), diverticulitis, cholecystitis, symptomatic cholangitis or appendicitis, acute pancreatitis or acute obstruction of the pancreatic duct or common bile duct, or gastric outlet obstruction

- ii. Abdominal fistula, GI perforation, bowel obstruction, intra-abdominal abscess within 6 months before randomization,

Note: Complete healing of an intra-abdominal abscess must be confirmed prior to randomization. Also no pre-existing fistula of head and neck area. No pre-existing ONJ.

- c. Other clinically significant disorders that would preclude safe study participation;

15. Major surgery within 12 weeks before the first dose of study treatment. Complete wound healing from major surgery must have occurred 1 month before the first dose of study treatment. Minor surgery (including uncomplicated tooth extractions) within 28 days before the first dose of study treatment with complete wound healing at least 10 days before the first dose of study treatment. Subjects with clinically relevant ongoing complications from prior surgery are not eligible;

16. QTcF > 500 msec within 1 month before the first dose of study treatment:

- a. Three ECGs must be performed for eligibility determination. If the average of these three consecutive results for QTcF is \leq 500 msec, the subject meets eligibility in this regard.

17. Pregnant or lactating females;

18. Inability to swallow intact tablets or inability to take pembrolizumab or cabozantinib

19. Previously identified allergy or hypersensitivity to components of the study treatment formulations;

20. Patients with a history of other prior malignancy must have been treated with curative intent and must have remained disease-free for 1 year post diagnosis. Patients with a prior history of squamous cell or basal carcinoma of the skin or in situ cervical cancer must have been curatively treated.

21. Patients with known history of interstitial lung disease or idiopathic pneumonitis.

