14. Female subjects of childbearing potential must not be pregnant at screening. Females of childbearing potential are defined as premenopausal females capable of becoming pregnant (ie, females who have had any evidence of menses in the past 12 months, with the exception of those who had prior hysterectomy). However, women who have been amenorrheic for 12 or more months are still considered to be of childbearing potential if the amenorrhea is possibly due to prior chemotherapy, antiestrogens, low body weight, ovarian suppression or other reasons.
15. A male participant must agree to use a contraception as detailed in this protocol during the treatment period and for at least during the active treatment plus an additional 90 days (a spermatogenesis cycle) for study treatments with evidence of genotoxicity at any dose] after the last dose of study treatment and refrain from donating sperm during this period.

Exclusion Criteria

1. Patients who have HPV negative squamous cell carcinoma of unknown primary in cervical lymph node.
2. The subject has received cytotoxic chemotherapy (including investigational cytotoxic chemotherapy) or biologic agents (eg, cytokines or antibodies) within 4 weeks, or nitrosoureas/mitomycin C within 6 weeks before the first dose of study treatment;
3. Prior treatment with cabozantinib or pembrolizumab; or any prior immunotherapy for treating squamous cell carcinoma of the head and neck;
4. Radiation therapy for bone metastasis within 2 weeks, any other external radiation therapy within 4 weeks before the first dose of study treatment. Systemic treatment with radionuclides within 6 weeks before the first dose of study treatment. Subjects with clinically relevant ongoing complications from prior radiation therapy are not eligible;
5. Receipt of any type of small molecule kinase inhibitor (including investigational kinase inhibitor) – such as VEGF inhibitors (examples, but not restricted to, sorafenib, sunitinib) within 14 days before the first dose of study treatment;
6. The subject has received any other type of investigational agent within 28 days or 5 half-lives, whichever is shorter, before the first dose of study treatment;

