3.3.2.14 Hemorrhagic Events

Hemorrhagic events have been reported with cabozantinib. In order to mitigate risk of severe hemorrhage, subjects should be evaluated for potential bleeding risk factors before initiating cabozantinib treatment and monitored for bleeding events with serial complete blood counts and physical examination while on study. Risk factors for hemorrhagic events may include (but may not be limited to) the following:

- Tumor of the lung with cavitary lesions or tumor lesions which invades, encases, major blood vessels. The anatomic location and characteristics of tumor as well as the medical history must be carefully reviewed in the selection of subjects for treatment with cabozantinib;
- Recent or concurrent radiation to the thoracic cavity;
- Active peptic ulcer disease, inflammatory GI diseases including Crohn's disease and ulcerative colitis;
- Underlying medical conditions which affect normal hemostasis (eg, deficiencies in clotting factors and/or platelet function, or thrombocytopenia);
- Concomitant medication with anticoagulants or other drugs which affect normal hemostasis;
- History of clinically significant hemoptysis.

The risk of hemorrhage in cabozantinib-treated subjects with brain metastases has not been thoroughly analyzed. Though the incidence of CNS hemorrhage events in a study of subjects with GB was higher than observed in general population of subjects with cancer treated with cabozantinib, it is not clear how the risk of hemorrhage in GB translates to a risk of hemorrhage for subjects with brain metastases. Currently, brain metastases of carcinomas are not contraindications to the use of cabozantinib, but subjects with brain metastases should be monitored with a high index of suspicion if symptoms that could be due to a CNS hemorrhage occur.

Cabozantinib should be discontinued in subjects with serious and life-threatening bleeding events or recent hemoptysis (≥ 2.5 mL of red blood).

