3.3.2.15 GI Perforation/Fistula and Non-GI Fistula Formation

Gastrointestinal perforation/GI fistula: Prior to initiation of treatment with cabozantinib, subjects should be carefully evaluated for potential risk factors including (but not limited to) the following:

- Tumors invading GI or respiratory tracts
- Active peptic ulcer disease, inflammatory bowel disease (eg, ulcerative colitis, Crohn's disease), diverticulitis, cholecystitis or symptomatic cholangitis, or appendicitis
- History of abdominal fistula, GI perforation, bowel obstruction, or intra-abdominal abscess
- Ongoing visceral complications from prior radiation therapy
- Prior GI surgery (particularly when associated with delayed or incomplete healing)

Complete healing following abdominal surgery and/or resolution of intra-abdominal abscess must be confirmed prior to initiating treatment with cabozantinib.

After starting cabozantinib, subjects should be monitored for early signs of GI perforation such as abdominal pain, nausea, emesis, constipation, and fever especially if known risk factors for developing GI perforation or fistula are present.

Discontinue cabozantinib treatment in subjects who have been diagnosed with GI perforation/fistula.

Non-GI fistula formation: Complications from radiation therapy has been identified as a possible predisposing risk factor for fistula formation in subjects undergoing treatment with cabozantinib.

Subjects with any clinically relevant ongoing complications from prior radiation therapy (ie, radiation esophagitis or other inflammation of the viscera) should not be treated with cabozantinib.

Radiation therapy to the thoracic cavity (including mediastinum) should be avoided within 3 months of starting treatment with cabozantinib (excluding local radiation for bone metastases). Fistula should be ruled out as appropriate in cases of onset of severe mucositis or difficulty swallowing after start of therapy. Discontinue cabozantinib and initiate appropriate management in subjects who have been diagnosed with a non-GI fistula.

Discontinue cabozantinib treatment in subjects who have been diagnosed with non-GI fistula.

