3.4 Concomitant Medications and Therapies

3.4.1 Anticancer Therapy

Local intervention is discouraged unless medically unavoidable. Subjects receiving local intervention (eg, palliative radiation) are allowed to continue to receive study treatment at the investigator's discretion.

Pembrolizumab Drug information:

Brand Names: US

Keytruda

Dosing: Adult

Head and neck cancer, squamous cell, recurrent or metastatic:

IV: 200 mg once every 3 weeks until disease progression, unacceptable toxicity, or (in patients without disease progression) for up to 24 months.

Dosing: Geriatric

Refer to adult dosing.

Dosing: Renal Impairment

No dosage adjustment necessary. In a pharmacokinetic study, no difference in clearance was noted for patients with eGFR ≥ 15 mL/minute/1.73 m².

Dosing: Hepatic Impairment

Hepatic impairment prior to treatment initiation:

Mild impairment (total bilirubin \leq ULN and AST $>$ ULN or total bilirubin $>$ 1 to 1.5 times ULN and any AST): No dosage adjustment necessary.

Moderate (total bilirubin $>$ 1.5 to 3 times ULN and any AST) to severe (total bilirubin $>$ 3 times ULN and any AST) impairment: There are no dosage adjustments provided in the manufacturer's labeling (has not been studied).

Hepatotoxicity during treatment:

Note: For patients with baseline grade 2 ALT or AST abnormalities due to liver metastases, permanently discontinue if AST or ALT increases by $\geq 50\%$ (relative to baseline) and persists at least 1 week.

AST or ALT $>$ 3 to 5 times ULN or total bilirubin $>$ 1.5 to 3 times ULN: Withhold treatment; may resume therapy upon recovery to grade 0 or 1 toxicity. Also administer corticosteroids (prednisone 0.5 to 1 mg/kg/day [or equivalent] followed by a taper).

AST or ALT $>$ 5 times ULN or total bilirubin $>$ 3 times ULN: Permanently discontinue. Also administer corticosteroids (prednisone 1 to 2 mg/kg/day [or equivalent] followed a taper).

Ocular toxicity: Optic neuritis which could manifest as a sudden onset of vision loss, loss of color vision, pain when moving eyes, and/or loss of peripheral vision. It may affect one or both eyes at the same time (optic neuritis).

Dosing: Adjustment for Toxicity

Withhold treatment for any of the following (may resume upon recovery to grade 0 or 1 toxicity):

Colitis, moderate (grade 2) or severe (grade 3); also administer corticosteroids (prednisone 1 to 2 mg/kg/day [or equivalent] followed by a taper).

Endocrinopathies:

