3.4.4 Prohibited or Restricted Therapies

The following therapies are prohibited while the subject is on study:

- Any investigational agent or investigational medical device;
- Any drug or herbal product used specifically for the treatment of SCCHN;

- Therapeutic doses of oral anticoagulants (eg, warfarin or other coumarin-related agents, direct thrombin or direct FXa inhibitors, or antiplatelet agents such as clopidogrel, or chronic use of aspirin above low dose levels for cardioprotection per local applicable guidelines);
- Any other systemic anticancer treatment (eg, chemotherapy, immunotherapy, radionuclides) and local anticancer treatment such as surgery, ablation, or embolization.

The following therapies should be avoided if possible, while the subject is on study:

- Palliative external radiation to bone metastasis for bone pain should not be performed while on study. Subjects who have such an intervention may be considered not evaluable (and may be assigned a censoring or progression date) for certain efficacy endpoints;
- Erythropoietic stimulating agents (eg, epoetin alfa and darbepoetin alfa) should not be used based on a report of increased risk of tumor recurrence and/or progression associated with erythropoietin(101);
- Chronic co-administration of cabozantinib with strong inducers of the CYP3A4 family (eg, phenytoin, carbamazepine, rifampin, rifabutin, rifapentine, phenobarbital, and St. John's Wort) may significantly decrease cabozantinib concentrations and should be avoided. Selection of alternate concomitant medications with no or minimal CYP3A4 enzyme induction potential is recommended;
- Caution must be used when discontinuing treatment with a strong CYP3A4 inducer in a subject who has been concurrently receiving a stable dose of cabozantinib, because this could significantly increase the exposure to cabozantinib;
- Co-administration of cabozantinib with strong inhibitors of the CYP3A4 family (eg, ketoconazole, itraconazole, clarithromycin, indinavir, nefazodone, nelfinavir, and ritonavir) may increase cabozantinib concentrations and should be avoided. Grapefruit and Seville oranges may also increase plasma concentrations of cabozantinib and should be avoided.

Additional information on potential drug interactions with cabozantinib is provided in Section 3.4.5.

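### Exclusion 4 permits the first dose 4 weeks after thoracic radiotherapy, while the fistula guidance in Section 3.3.2.15 advises 3 months; no eligibility item carries the longer interval

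*Combined protocol and SAP*

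**What the plan says.** **Eligibility.** Section 4, Exclusion Criteria, item 4, bars "Radiation therapy for bone metastasis within 2 weeks, any other external radiation therapy within 4 weeks before the first dose of study treatment". The synopsis has the same limit: "any other external radiation therapy within 4 weeks before the first dose of study treatment". Neither has a separate rule for the chest. Inclusion 5 sets intervals to registration: 4 months after head and neck radiotherapy combined with chemotherapy, 8 weeks after head and neck radiotherapy alone, and 3 weeks after radiation elsewhere. It also asks for healed treatment areas without sequelae that favour fistula. Exclusion 4 removes patients with relevant ongoing radiation complications.

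**Guidance.** Section 3.3.2.15 says: "Radiation therapy to the thoracic cavity (including mediastinum) should be avoided within 3 months of starting treatment with cabozantinib (excluding local radiation for bone metastases"). The paragraph opens by stating that complications of radiation therapy form a factor that "has been identified as a possible predisposing risk factor for fistula formation in subjects undergoing treatment with cabozantinib". The sentence just before the 3-month advice says which patients with radiation complications should not receive cabozantinib.

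**Related text.** Section 3.3.2.14 names "Recent or concurrent radiation to the thoracic cavity" among the bleeding risk factors, without an interval. It adds that tumor location and characteristics, and "the medical history must be carefully reviewed in the selection of subjects for treatment with cabozantinib".

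**The concern.** The protocol holds two time limits that bear on the same patient, and only the shorter one is an eligibility criterion. Section 16 (Pre-Treatment Period) makes eligibility depend on the inclusion and exclusion lists. The 3-month advice sits in the adverse-event management text, where someone checking eligibility may not look, and the two sites could apply it differently.

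At stake is a patient who looks healed at, say, week 5. Criteria based on visible damage will not stop that patient from being dosed; an interval would. The outcome the advice is meant to prevent is serious: Section 3.3.2 requires permanent discontinuation of cabozantinib for fistula formation.

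**Working it through.** The plan gives no figure to reproduce. The check compares the intervals and then reads the guidance sentence for its direction.

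**1. Intervals in days**, taking 3 months as 365.25/4 and 4 months as 365.25/3:

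| Situation | Source | Interval | Counted to |
|---|---|---|---|
| Non-bone external radiation, any site | Exclusion 4 | 4 × 7 = 28 | first dose |
| Radiation outside head and neck | Inclusion 5 | 3 × 7 = 21 | registration |
| Head and neck radiation alone | Inclusion 5 | 8 × 7 = 56 | registration |
| Head and neck chemoradiation | Inclusion 5 | 365.25/3 = 121.8 | registration |
| Major surgery | Exclusion 15 | 12 × 7 = 84 | first dose |
| Thoracic radiation, non-bone (advice) | Section 3.3.2.15 | 365.25/4 = 91.3 | start of cabozantinib |

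**2. Uncovered period.** 91.3 − 28 = 63.3 days, and 63.3/7 = 9.0 weeks. It runs from about week 4 to week 13 after the end of thoracic radiation. The 21-day rule is shorter and does not narrow it. The 8-week and 4-month rules apply to head and neck radiotherapy, not to separate lung or mediastinal fields.

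**3. Search for another criterion with the interval.** The 3-month look-backs in the exclusion list concern hemoptysis and other signs of pulmonary hemorrhage (10b and 10c). None concerns thoracic radiotherapy. The healing rule (inclusion 5), recovery from earlier toxicity (inclusion 10), the bar on ongoing complications (exclusion 4) and the general clause (14c) set no interval.

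**4. Direction of the 3-month advice.** Three readings are possible:

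- Before the start only: the 63-day gap exists.
- Both sides of the start: the pre-dose period is included, so the same gap exists.
- After the start only: there is no eligibility gap.

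Two features favour a reading that includes the pre-dose period. The paragraph presents radiation complications as predisposing, and the advice directly follows a sentence on whom not to treat, which is patient selection.

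**5. How the protocol treats similar risks.** After major surgery it asks for 12 weeks as well as complete wound healing. After head and neck radiation it asks for 8 weeks or 4 months as well as healed fields. After thoracic radiation it asks for healed fields, but only the general short interval.

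**The case against.** **The direction is not settled.** The advice does not say before or after. The next sentence in Section 3.3.2.15 concerns events once therapy has begun, and Section 3.3.2.14 speaks of concurrent as well as recent radiation. A reader might argue that on-study radiation has its own rules elsewhere, so the 3 months must lie before the first dose. The documents do not bear this out. The item on external radiation in Section 3.4.4, "Palliative external radiation to bone metastasis for bone pain should not be performed while on study", covers bone metastases only, which is what Section 3.3.2.15 excepts. Section 3.4.1, "Subjects receiving local intervention (eg, palliative radiation) are allowed to continue to receive study treatment" at the investigator's discretion, is general and does not mention the chest. The pre-dose reading rests on the wording around the advice alone. It is the better reading, but not a certain one.

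**A minimum and a piece of advice can coexist.** Exclusion 4 sets a floor, and Section 3.3.2.15 adds caution for the same investigator. Meeting the floor does not cancel the advice. This stands: the two provisions are not aligned, but a reader who infers a direct contradiction goes too far.

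**Binding criteria already address the hazard.** Besides the healing and complication rules, exclusions 10 to 13 remove patients with recent clinically significant gastrointestinal bleeding, hemoptysis or pulmonary hemorrhage, cavitating lung lesions, invasion or encasement of major vessels, invasion of the gastrointestinal tract, or endotracheal or endobronchial tumor. This reduces the risk and leaves a narrow group, but it does not supply the interval.

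**The parallels prove little.** The bleeding list gives no interval, so it cannot support 3 months, and the surgery interval is an analogy. This is correct. The 3-month figure comes from Section 3.3.2.15 alone.

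**Conclusion.** The concern holds as an advisory precaution that the eligibility criteria do not carry. A patient about 4 to 13 weeks after non-bone thoracic radiation, with healed fields and no ongoing complications, passes every radiotherapy window during about 63 days in which the protocol's own fistula guidance advises against such radiation.

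This assumes that the 3 months include the time before the first dose; if they run only from the start of treatment, just the ambiguity of wording remains. The eligibility checklist mentioned in Section 2.6 is not reproduced and may already cover the point.

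The documents do not say how many patients would fall in the gap; the number is probably small. A reader might also infer harm to the trial's statistical conclusions. There is no basis for that: the sample size, the interim rule and the final decision rule do not depend on this interval. The point is a cheap improvement to patient safety.

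**What to change.** Add to exclusion 4, in Section 4 and in the synopsis: *radiation to the thoracic cavity or mediastinum in the 3 months before first study dose, unless given locally for bone metastases*. In Section 3.3.2.15, state that the 3 months are counted before the first dose. Add a line to the eligibility checklist if it lacks one. Leave the 2-week bone window and the 3-week registration rule as they are.

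The cost is one clause in two places, a few words of clarification and perhaps a checklist line. The real price falls on a few patients, who would wait up to about 9 weeks more. Inclusion 8 requires a life expectancy of only more than 3 months. For a patient at that limit, the longest wait is 63.3/91.3, or about 69% of the expected time, which in practice is exclusion.

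A lighter option is to clarify the direction in Section 3.3.2.15 and refer to it from exclusion 4. That keeps investigator discretion, but leaves the interval outside the binding criteria.
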